**OBJECTIVES:**

The primary objectives of the study are to:

- Evaluate the efficacy of UX007 compared to placebo as measured by the reduction from

randomization to week 8 in frequency of seizures. Observable generalized and partial-onset seizures measured for 6 weeks by diary and absence seizures measured overnight by electroencephalography (EEG).

- Evaluate the safety of UX007 via adverse event (AE) rates, laboratory values, and electrocardiogram (ECG)

The secondary objectives of the study are to:

- Evaluate the efficacy of UX007 compared to placebo, as measured by:
  - Seizure response rate, defined as the percentage of subjects with at least 50% reduction from randomization to week 8 in frequency of seizures
  - Change from randomization to Week 8 in cognitive function using the Cambridge Neuropsychological Test Automated Battery (CANTAB)
  - Change from randomization to Week 8 in distance walked as measured by 6MWT
  - Time to onset of paroxysmal exertional dyskinesia (PED) as measured during 6MWT from randomization to Week 8
  - Change from randomization to Week 8 in gross motor function using the Gross Motor Function Measure-88 (GMFM-88)
- Evaluate long-term efficacy as measured by changes from randomization in frequency of seizures over time through Week 52
- Evaluate the optimal dose to control seizures and impact on other clinical manifestations during the Dose Exploration Period

Exploratory objectives are to:

- Evaluate the effects of UX007, from randomization through Weeks 8 and 52 on:
  - Neurological function using the Columbia Neurological Score (CNS)
  - Physician global impression of change in clinical status using the Clinical Global Impression - Severity scale (CGI-S) and Clinical Global Impression - Improvement scale (CGI-I)
  - Receptive vocabulary using the Peabody Picture Vocabulary Test (PPVT)
  - Subject or caregiver-reported quality of life using Short Form-10™ (SF-10) Health Survey for Children or SF-12 for adults
  - Functional disability by caregiver report using the Pediatric Evaluation of Disability

Inventory – Computer Adaptive Test (PEDI-CAT)

- Gait, using gait analysis by computerized mat
- PK properties of UX007 and its metabolites

Exploratory objectives are to evaluate the effects of UX007, from randomization through Weeks 8 and 52 on (to be administered at select sites):

- Visual motor integration using the Beery-Buktenica Developmental Test of Visual Motor Integration (Beery-VMI)

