### 7.3.1 Inclusion Criteria

Individuals eligible to participate in this study must meet all of the following criteria:

- 1) Diagnosis of Glut1 DS confirmed by *SLC2A1* mutation
- 2) Males and females at least 1 year of age at the time of informed consent
- 3) Average of at least 2 observable seizures (generalized or partial-onset [simple partial motor, complex partial, absence, or secondarily generalized] seizures) in 4 weeks over the last 24 weeks, by subject or caregiver report
- 4) At least 2 observable seizures (generalized or partial-onset [simple partial motor, complex partial, or secondarily generalized] seizures) in 4 weeks during the baseline period, with no 3-week seizure-free period during the Baseline Period OR absence seizures documented on Screening EEG
- 5) Continuing to have seizures despite a prior or current use of at least 1 AED
- 6) Allowed to be on up to 3 concomitant AEDs that must have been stable in dose at least 2 weeks prior to the beginning of screening and anticipated to remain stable in dose through the end of the 8-week, placebo-controlled Treatment Period
- 7) Not on, or not fully compliant with a prescribed diet plan (e.g. KD)
- 8) Plasma level of beta-hydroxybutyrate (BHB)  $\leq 1$  mmol/L (non-fasting) at Screening
- 9) Provide written or verbal assent (if possible) and written informed consent by a legally authorized representative after the nature of the study has been explained, and prior to any research-related procedures
- 10) Must, in the opinion of the investigator, be willing and able to complete all aspects of the study, comply with accurate completion of the seizures diary, and likely to complete the 8-week, placebo-controlled, Treatment Period
- 11) Females of childbearing potential must have a negative pregnancy test at Screening, be willing to use an acceptable method of contraception, and have additional

pregnancy tests during the study. Females considered not of childbearing potential include those who have not reached menarche, had total hysterectomy, have been in menopause for at least two years, or have had tubal ligation at least one year prior to Screening.

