### 7.5.2.1 Primary Efficacy Variable

**Seizure Frequency Reduction:** Percent reduction from randomization to week 8 in frequency of seizures. Observable generalized and partial-onset seizures measured for 6 weeks by diary and absence seizures measured overnight by electroencephalography (EEG).

Seizures are a hallmark of Glut1 DS in approximately 90% of affected individuals ([Wang et al. 2012](#)). The frequency of seizures varies among individuals; some experience daily events while others may have seizures separated by days, weeks, or even months. The number of observable seizures will be recorded by the subject or caregiver via diary throughout the study.

The frequency of different seizure types will be recorded. Seizure types will be defined and standardized according to the ILAE Commission on Classification and Terminology ([Berg et al. 2010](#)). Indicated seizure types are consistent with those observed in a large Glut1 DS cohort study designed to define epilepsy phenotypes in this population ([Pong et al. 2012](#)).

Observable seizures for the primary efficacy measure are defined as:

- Generalized Tonic-Clonic, Generalized Tonic, Generalized Clonic, Generalized Atonic
- Partial/Focal with Secondary Generalization
- Myoclonic, Myoclonic (Astatic) Atonic, Myoclonic Tonic
- Complex Partial/Focal
- Simple Partial/Focal Motor

**Electroencephalography:** Case-report studies in limited groups of Glut1 DS patients suggest a normal interictal background is the most common finding on both routine and prolonged EEG recordings. Both absence and myoclonic seizures have been observed in pediatric Glut1 DS patients during overnight continuous monitoring ([Leary et al. 2003](#)).

Several studies have examined electrophysiologic characteristics in Glut1 DS patients on KDs (Kessler et al. 2011).

Abnormalities on EEG (including absence seizures) will be recorded with an overnight EEG conducted at the Week 0, 8, 26, and 31 visits. Confirmatory EEG at Screening for patients with absence seizures only is required for ~3 hours. For Week 0 EEG, begin EEG PRIOR TO Randomization date. Monitoring periods of less than 12 hours in duration for Week 0, 8, 26, and 31 visits will be considered a protocol violation. Key measures will include: (1) frequency of EEG seizures, including absence; and (2) frequency of interictal epileptiform discharges.

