#### **7.6.4 Secondary Efficacy Analyses**

The secondary efficacy analyses are primarily focused on alternative domains of Glut1 DS disease to assess the breadth of treatment effect of UX007. The secondary analyses will compare the secondary efficacy variables scores after treatment to before treatment between the treated and placebo groups. The specific tests and analyses will be defined in the SAP.

Included in these analyses will be a predefined per protocol analysis of those subjects that achieve at least 30% of calorie intake or higher as the tolerated dose level and have received at least 80% of the expected doses, to assess whether a subpopulation of the highest dose subjects have a larger difference in efficacy.

In general, each of the efficacy variables assessed at Week 52 (or Week 26 for EEG only) will be compared to the value obtained during the Baseline Period or Randomization (i.e., Screening visit if not performed at the Baseline visit) utilizing the same statistical test as conducted at the Week 8 analysis, but adjusted for the difference that the analyses for the Week 52 data will only utilize a within-cohort comparison and not a between-cohort comparison.

Secondary endpoints evaluating the efficacy of UX007 compared to placebo will include:

- Seizure response rate, defined as the percentage of subjects with at least 50% reduction from randomization to week 8 in frequency of seizures
- Observable seizure frequency reduction and observable seizure response rate as measured by diary
- Absence seizure frequency reduction and absence seizure response rate as measured by EEG
- Change from randomization to Week 8 in cognitive function using the CANTAB
- Change from randomization to Week 8 in distance walked as measured by 6MWT
- Time to onset of PED as measured during 6MWT from randomization to Week 8
- Change from randomization to Week 8 in gross motor function using the GMFM-88
- Long term efficacy as measured by changes from randomization in frequency of generalized or partial-onset seizures over time through week 52
- Optimal dose to control seizures and impact on other clinical manifestations during the Dose Exploration Period

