4.1 Primary Efficacy Endpoint

The primary endpoint to evaluate the efficacy of UX007 in Glut1 DS is as follows:

- Reduction from baseline to week 8 in frequency of seizures (normalized to a 4-week rate): observable seizures measured for 6 weeks after 2-week titration by diary and absence seizures measured overnight by electroencephalography (EEG). The primary efficacy endpoint will be derived for each subject based on subject seizure type at randomization: observable seizures from the diary will be used for Observable Seizures Subjects and absence seizures from EEG will be used for Absence Seizures Only Subjects (see Section 5.6).

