4.2 Secondary Efficacy Endpoints

The following are considered secondary endpoints to evaluate the efficacy of UX007 in Glut1 DS:

- Reduction from baseline to week 8 in frequency of observable seizures (normalized to a 4-week rate) measured for 6 weeks after 2-week titration by diary
- Reduction from baseline to week 8 in frequency of absence seizures (normalized to a 4-week rate) measured overnight by EEG
- Seizure response at Week 8, defined as at least 50% reduction from baseline to week 8 in frequency of seizures
- Observable seizure response at Week 8, defined as at least 50% reduction from baseline to week 8 in frequency of observable seizures measured by diary
- Absence seizure response at Week 8, defined as at least 50% reduction from baseline to week 8 in frequency of absence seizures measured overnight by EEG
- Cognitive function using the Cambridge Neuropsychological Test Automated Battery (CANTAB): change from baseline to Week 8 in the following scores:
 - Reaction Time (RTI):
 - Simple Choice Median Reaction Time (RTIMDSRT)
 - Five Choice Median Reaction Time (RTIMDFRT)
 - Simple Choice Standard Deviation (RTISRTSD)
 - Spatial Span (SSP):
 - Span Length (SSPSLF)
 - Paired Associates Learning (PAL):
 - Total Errors (Adjusted) (PALTEA)
 - First Trial Memory Score (PALFTMS)

- Spatial Working Memory (SWM):
 - Between Errors (SWMBE48)
 - Strategy (SWMS68)
- Change from baseline to Week 8 in distance traveled (in meters) as measured by 6MWT
- Change from baseline to Week 8 in distance traveled (in percent predicted) as measured by 6MWT
- Time (in minutes) to onset of paroxysmal exertional dyskinesia (PED) as measured during 6MWT through Week 8
- Gross motor function using the Gross Motor Function Measure-88 (GMFM-88): change from baseline to Week 8 in Total Score.
- Reduction from baseline over time in frequency of seizures (normalized to a 4-week rate): observable seizures measured daily by diary and absence seizures measured overnight by electroencephalography (EEG)
- Reduction from baseline over time in frequency of observable seizures (normalized to a 4-week rate) measured daily by diary
- Reduction from baseline over time in frequency of absence seizures (normalized to a 4-week rate) measured overnight by EEG

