8.6.2 Estimation by Treatment Group and Overall

Estimation by randomized treatment group, for subjects while taking UX007 and overall will be done over time will be analyzed using a generalized estimation equations (GEE) model as follows:

- Continuous endpoints will be analyzed using a GEE linear model, with change from baseline at each timepoint as the response variable; treatment group (UX007 vs. placebo), a factor for visit, visit by treatment interaction and an appropriate baseline value as covariates; identity link function and exchangeable within subject working correlation matrix.
- Categorical (binary) endpoints will be analyzed using a GEE logistic model, with a yes/no indicator at each timepoint as the response variable; treatment group (UX007 vs. placebo), a factor for visit, visit by treatment interaction and an appropriate baseline value as covariates, logit link function and exchangeable within subject working correlation matrix.

All available measurements during the appropriate study period will be included in the model.

If the number of observations is insufficient for analyses, summary statistics will be provided.

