APPENDIX A EFFICACY ENDPOINT SUMMARY TABLE

Test / Instrument	Eligible Study Population	Endpoint	Subjects Applicable	Endpoint Level	Timepoints for Assessments	Statistical Approach: Week 8 Analyses	Statistical Approach: Week 52 Analyses
Seizure Diary + EEG	Efficacy Analysis Set	Reduction from baseline in frequency of seizures	All	Primary	Diary: daily from Screening to 52/ET; EEG: Screening, Randomization, Week 8, 26, 31	ANCOVA	Estimation
Seizure Diary + EEG	Efficacy Analysis Set	Seizure response	All	Secondary	Diary: daily from Screening to 52/ET; EEG: Screening, Randomization, Week 8, 26, 31	Logistic Regression	Estimation
Seizure Diary	Efficacy Analysis Set – Observable Seizures	Reduction from baseline in frequency of observable seizures	All	Secondary	Daily from Screening to 52/ET	ANCOVA	Estimation
Seizure Diary	Efficacy Analysis Set – Observable Seizures	Observable seizure response	All	Secondary	Daily from Screening to 52/ET	Logistic Regression	Estimation
EEG	Efficacy Analysis Set – Absence Seizures	Reduction from baseline in frequency of absence seizures	All	Secondary	Screening, Randomization, Week 8, 26, 31	ANCOVA	Estimation
EEG	Efficacy Analysis Set – Absence Seizures	Absence seizure response	All	Secondary	Screening, Randomization, Week 8, 26, 31	Logistic Regression	Estimation
CANTAB	Efficacy Analysis Set	Change from baseline in CANTAB RTI Simple Choice Median Reaction Time (RTIMDSRT)	All	Secondary	Screening, Randomization, Week 4, 8, 26, 31, 36, 52, ET	GEE Linear	Estimation

Test / Instrument	Eligible Study Population	Endpoint	Subjects Applicable	Endpoint Level	Timepoints for Assessments	Statistical Approach: Week 8 Analyses	Statistical Approach: Week 52 Analyses
CANTAB	Efficacy Analysis Set	Change from baseline in CANTAB RTI Five Choice Median Reaction Time (RTIMDFRT)	All	Secondary	Screening, Randomization, Week 4, 8, 26, 31, 36, 52, ET	GEE Linear	Estimation
CANTAB	Efficacy Analysis Set	Change from baseline in CANTAB RTI Simple Choice Standard Deviation (RTISRSD)	All	Secondary	Screening, Randomization, Week 4, 8, 26, 31, 36, 52, ET	GEE Linear	Estimation
CANTAB	Efficacy Analysis Set	Change from baseline in CANTAB SSP Span Length (SSPSLF)	All	Secondary	Screening, Randomization, Week 4, 8, 26, 31, 36, 52, ET	GEE Linear	Estimation
CANTAB	Efficacy Analysis Set	Change from baseline in CANTAB PAL Total Errors (Adjusted) (PALTEA)	All	Secondary	Screening, Randomization, Week 4, 8, 26, 31, 36, 52, ET	GEE Linear	Estimation

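### At visits without EEG the combined long-term seizure endpoint rests on diary-based subjects only, so its time trend may partly reflect case mix

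*Protocol*

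**What the plan says.** **EEG schedule.** Protocol 7.5.2.1 has "overnight EEG conducted at the Week 0, 8, 26, and 31 visits", apart from a short confirmatory Screening EEG. SAP Appendix A lists the same visits beside the combined endpoint ("EEG: Screening, Randomization, Week 8, 26, 31"), while the diary runs daily to Week 52 or early termination.

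**Who depends on EEG.** Protocol 7.3.1 admits subjects with "OR absence seizures documented on Screening EEG". SAP 4.1 states that "absence seizures from EEG will be used for Absence Seizures Only Subjects". SAP 5.7.5 does not count the diary's absence codes (M to P) as observable seizures. Under SAP 5.6 and 6.3.4 the absence-only group also includes some subjects with a few observable seizures.

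**Long-term analysis.** The protocol objective is: "Evaluate long-term efficacy as measured by changes from randomization in frequency of seizures over time through Week 52". SAP 4.2 lists the combined endpoint over time as secondary. Appendix A plans Week 52 estimation of combined frequency and combined response in the Efficacy Analysis Set, and SAP 8.6.3 adds a by-visit summary over the entire study. In SAP 8.6.2 the model is a GEE with treatment, visit, their interaction, baseline and exchangeable correlation: "All available measurements during the appropriate study period will be included in the model". SAP 7.1 rules out imputation in the open-label period.

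**Seizure type.** SAP 8.6.3 and 8.6.4 require the absence-only indicator in the Week 8 models of combined frequency and combined response. SAP 4.5 permits it in general. Section 8.6.2 does not name it.

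**The concern.** Taken together, these rules change who is measured from visit to visit. Everyone can contribute at Weeks 8, 26 and 31. At Weeks 14, 36, 44 and 52 the absence-only subjects have no value, by design. No rule says what the combined endpoint means at those visits.

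Whether a value is missing depends on seizure type, and type is not in the long-term model. If response also depends on type, visit means shift when the composition shifts, even though no subject has changed. The baseline covariate is a poor substitute for type, because it mixes diary counts per 28 days (SAP 5.7.1) with EEG counts per 24 hours (SAP 5.7.2).

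At stake is the claim of persistence. A lower value at Week 52 than at Week 26 could be read as waning, and a higher one as continued gain, when either could come from the change in who is measured. The last EEG also falls in the Dose Exploration Period, so no EEG is scheduled on the dose maintained afterwards.

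**Working it through.** **The plan's own figure.** The documents give no figure for the long-term endpoint. Their stated power concerns Week 8 and reproduces. With 30:10 subjects, a difference of 50 and SD 55, the SE is 55 × √(1/30 + 1/10) = 20.08, and 50/20.08 − 1.645 = 0.845. This gives power 0.801 (0.788 by noncentral t) against the stated approximately 80%.

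**Step 1: who can contribute** (Protocol Table 2.1; SAP 4.1 and Appendix A).

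| Week | 8 | 14 | 26 | 31 | 36 | 44 | 52 |
|---|---|---|---|---|---|---|---|
| Observable Seizures Subjects (diary) | yes | yes | yes | yes | yes | yes | yes |
| Absence Seizures Only (EEG) | yes | no | yes | yes | no | no | no |

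Subjects with both seizure types stay in throughout, through the diary.

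**Step 2: unadjusted by-visit summary.** Let p be the absence-only share, and let rA and rO be the constant true reductions in absence-only and observable subjects. On the log scale, ignoring the +1 offset:

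- with EEG: combined reduction = 1 − exp[p·ln(1 − rA) + (1 − p)·ln(1 − rO)]
- without EEG: combined reduction = rO

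The documents give none of these inputs, so every value below is an assumption.

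- p = 0.3, rA = 50%, rO = 0%: 0.3 × ln 2 = 0.208 and 1 − exp(−0.208) = 18.8%, falling to 0%. The arithmetic mean of percent reductions would go from 0.3 × 50% = 15% to 0%.
- Other values:

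| rA / rO | p | EEG visits | Other visits | Shift (points) |
|---|---|---|---|---|
| 60% / 20% | 0.1 | 25.4% | 20.0% | −5.4 |
| 60% / 20% | 0.2 | 30.4% | 20.0% | −10.4 |
| 60% / 20% | 0.4 | 39.4% | 20.0% | −19.4 |
| 20% / 40% | 0.2 | 36.4% | 40.0% | +3.6 |
| 20% / 40% | 0.4 | 32.7% | 40.0% | +7.3 |
| 30% / 30% | any | 30.0% | 30.0% | 0 |

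**Step 3: the GEE.** The Section 8.6.2 model was simulated with a visit factor, baseline and exchangeable correlation, N = 40 and constant true effects. The treatment terms were left out for simplicity.

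- p = 0.3, 50% against 0%, residual log SD 0.8, within-subject correlation 0.3 to 0.7. Without a type term, the estimate goes from about 18–21% at Week 26 to about 11–18% at Week 52; the fall is larger at the lower correlation. With the type term it is flat at about 18–19%.
- p = 0.4, 60% against 20%, residual log SD 0.6, correlation 0.5. Without the term, about 39% at Weeks 8, 26 and 31 becomes about 35% at Weeks 14, 36, 44 and 52. With the term it is about 39% throughout.
- Across the unequal-effect scenarios at residual log SD 0.6, the shift was about 1 to 4 points.

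The GEE borrows from each subject's other visits, which reduces the shift without removing it. The by-visit summary has no such protection.

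**The case against.** The strongest reply is that the plan discloses the schedule and already separates the seizure types. Protocol 7.6.4 qualifies the Week 52 comparison with "or Week 26 for EEG only", Appendix A prints the EEG visits next to the combined endpoint, and SAP 4.2 lists observable and absence seizures over time as endpoints of their own. SAP 4.5 allows the type indicator. The analysis is secondary, open-label and estimation only, in a Phase 2 study. All of this is correct. It limits the weight of the point and makes the repair cheap. It does not say what the combined endpoint means at a visit without EEG, and it does not put the indicator into Section 8.6.2.

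A reader might infer more than the documents support:

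- **That the modelled effect would fall from 19% to nothing.** That figure belongs to the unadjusted by-visit summary under one extreme assumption. The GEE shift is smaller.
- **That the trend is certainly biased, or biased downwards.** Bias needs effects that differ by type. A larger effect on observable seizures reverses the direction.
- **That absence-only subjects have no assessment to Week 52.** The diary continues and records absence codes. What stops at Week 31 is EEG measurement, the only source for these subjects in the combined endpoint.

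**Conclusion.** The point stands as a gap in the secondary long-term analysis. Followed as written, the plan produces a combined time course whose population changes at Weeks 14, 36, 44 and 52, with no rule or model term to account for it. That follows from the schedule and the endpoint derivation and needs no assumption.

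The size of any distortion does rest on assumptions. With 10–40% absence-only subjects and the 60/20 and 20/40 effect pairs, the by-visit summary shifts by between −19.4 and +7.3 points. In the GEE the shift was about 1 to 4 points in those settings at p = 0.2 and 0.4, and larger in the 50/0 illustration at low within-subject correlation. It is zero if effects are equal. The change should be made before the long-term results are reported. The Week 8 primary analysis is unaffected, because EEG and diary are both available then.

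**What to change.** No new procedure is needed.

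1. Report the combined over-time frequency and response endpoints only at Weeks 8, 26 and 31, noting that Week 31 falls in the Dose Exploration Period.
2. At Weeks 14, 36, 44 and 52, report observable seizure frequency in Observable Seizures Subjects, using the separate over-time endpoint already in SAP 4.2. SAP 5.7.1 defines diary windows only up to Week 8, so add the later ones.
3. Put the Absence Seizures Only indicator in the Section 8.6.2 models of the combined endpoints. It does not replace item 1: at a visit without EEG it assumes that the difference between types seen at the EEG visits still holds, which the data cannot check.
4. Show the number of subjects by seizure type at every visit, in the model output and in the Section 8.6.3 summary.
5. State that long-term conclusions run to Week 52 for observable seizures and only to the last EEG visits for EEG-measured absence seizures, in line with Protocol 7.6.4, and align the objective with that.

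The cost is wording in the SAP and the objective, plus a column of counts. The real price is that the combined long-term claim narrows.
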